8.1. Study Design

Study objectives will be evaluated through an observational analysis of a clinical cohort utilizing prospectively-collected EMR data obtained from the OPERA Observational Database. Study participants will be identified from the most recent database build available.

Period of subject inclusion:

- 01AUG2013 (DTG-approval)
- 31DEC2017

Period of observation:

- 01AUG2013 (DTG-approval)
- 31DEC2018

Population:

- A diagnosis of HIV-1, a positive HIV-1 Western Blot, or a positive HIV-1 enzymelinked immunosorbent assay (ELISA); and a detectable HIV-1 viral load test
- At least 18 years of age at the index date
- Male or female
- Prescribed one of the following core agents as part of a 3-drug regimen for the first time between 01AUG2013 and 31DEC2017:
 - DTG (Tivicay[®], Triumeq[®])
 - RPV (Edurant[®], Complera[®], Odefsey[®])
 - RAL (Isentress[®], Isentress HD[®])
 - EVG/c (Vitekta[®], Stribild[®], Genvoya[®])
 - DRV (/r/c) (Prezista[®], Prezcobix[®], Symtuza[®])
 - BIC (Biktarvy[®])
- Not exposed to >1 core agent of interest concurrently

Index date: The index date for an eligible patient is defined as the first date of the first regimen of interest ever prescribed to a patient after 01AUG2013.

Baseline period: The 12-month baseline period preceding the index date will be used to assess patient demographic and clinical characteristics. Data from the visit closest to the index date will be used for analysis.

Observation period: Patients will be observed from their index date until 6,12, and 24 months post-initiation of the regimen of interest, with the final study end date on 31DEC2018.

Censoring events: (i) End of follow-up (6,12, or 24 months after core agent initiation), (ii) cessation of continuous clinical activity*, (iii) core agent discontinuation, (iv) pregnancy, (v) death, or (vi) study end (31DEC2018).

* Continuous clinical activity is defined as at least one clinic visit within a 12month period. Patients failing to meet the continuous clinical activity requirement will be censored 12 months after their last contact.

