8.3.2. Outcomes of Interest

- 1. BMI/weight:
 - Weight (in kg) will be assessed at baseline, and at 6 months, 12 months, and 24 months after core agent initiation
 - BMI will be assessed at baseline, and at 6 months, 12 months, and 24 months after core agent initiation. BMI will be defined as:
 - $BMI = weight/height^2$
 - Weight measured in kg
 - Height measured in m
 - Baseline BMI identified using weight measured within 3 months prior to or on index date
 - BMI categories will be assessed at baseline, and at 6 months, 12 months, and 24 months after core agent initiation (shown in Table 11)
 - Changes in BMI after 6 months, 12 months, and 24 months on the core agent of interest will be calculated as:
 - $\Delta BMI = BMI_n BMI_0$
 - Where BMI_n is BMI at 6, 12, or 24 months and BMI₀ is BMI at baseline
 - Changes in weight after 6 months, 12 months, and 24 months on the core agent of interest will be calculated as:
 - $\Delta Weight = Weight_n Weight_0$

Where Weight_n is weight at 6, 12, or 24 months and Weight₀ is Weight at baseline

- Time windows for BMI and weight
 - BMI/weight at 6 months: BMI measured the closest to 6 months after core agent initiation, between >3 and ≤9 months
 - BMI/weight at 12 months: BMI measured the closest to 12 months after core agent initiation, between >9 and ≤15 months
 - BMI/weight at 24 months: BMI measured the closest to 24 months after core agent initiation, between >21 and ≤27 months
- 2. Total cholesterol/HDL/LDL/triglycerides:

- Lipids (total cholesterol, HDL, LDL, triglycerides) will be assessed at baseline and at 6 months, 12 months, and 24 months after core agent initiation
- Time windows for lipid panels
 - Lipids at 6 months: lipids measured the closest to 6 months after core agent initiation, between >3 and ≤9 months
 - Lipids at 12 months: lipids measured the closest to 12 months after core agent initiation, between >9 and ≤15 months
 - Lipids at 24 months: lipid measured the closest to 24 months after core agent initiation, between >21 and ≤27 months
- Total cholesterol levels¹
 - Normal: < 5.2 mmol/L or <200 mg/dl

 - Borderline Abnormal: ≥ 5.2 to < 6.2 mmol/L or ≥ 200 to < 240 mg/dl
 - Dyslipidemia: ≥ 6.2 to < 7.2 mmol/L or ≥ 240 to < 280 mg/dl
 - Severe dyslipidemia: ≥ 7.2 mmol/L or ≥ 280 mg/dl
- LDL levels¹
 - Normal: < 2.5 mmol/L or <100 mg/dl

 - Borderline Abnormal: ≥ 2.5 to < 3.3 mmol/L or ≥ 100 to < 130 mg/dl
 - Dyslipidemia: ≥ 3.3 to < 4.1 mmol/L or ≥ 130 to < 160 mg/dl

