8.5. Data analysis

For each time point assessed (6,12, or 24 months), the study population will be restricted to patients with a follow-up greater or equal to that time point.

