8.5.1. Analysis of primary objectives

Baseline descriptive analyses of demographic and clinical characteristics

Descriptive statistics will be conducted for patients prescribed a core agent of interest between 01AUG2013 and 31DEC2017. All baseline covariates listed in sections 8.3.2. and 8.3.3. will be described, as well as baseline BMI, weight, lipodystrophy and lipid panels; medians and interquartile ranges for continuous variables and counts and percentages for categorical variables will be provided. Pairwise comparisons between DTG and each of the other core agent groups will be evaluated by p-values calculated from the Pearson Chi-Square test for categorical variables. The Fisher's exact test will be used to compare frequencies with few events. The Wilcoxon Rank Sum test will be used to calculate p-values for continuous variables.

Description of follow-up levels of total cholesterol, HDL, LDL, triglycerides, weight and BMI

Lipids (total cholesterol, HDL, LDL, triglycerides), weight and change in weight, and BMI and change in BMI will be assessed continuously and compared between patients for each core agent at 6,12, and 24 months after initiation. BMI and lipids will also be assessed categorically, as the proportion of patients in each BMI and lipid category and the proportion of patients changing categories of BMI (see section 8.3.2 for a definition of changes in categories). Given that the data reflect routine clinical care, not all patients will have the lab values of interest at each time point. The denominator for proportions will be patients tested, excluding those with missing values. Pairwise comparisons will be performed using Pearson Chi-Square test or Fisher's exact test for categorical variables and Wilcoxon Rank Sum test for continuous variables.

Description of existing lipodystrophy at core agent initiation and new diagnoses of lipodystrophy

Existing lipodystrophy will be assessed as the proportion of patients diagnosed with lipodystrophy 12 months prior to or on the index date among patients initiating each core agent of interest. New cases of lipodystrophy will be assessed as the proportion of patients who develop lipodystrophy at 6,12, or 24 months after initiation among patients without lipodystrophy at baseline. Pairwise comparisons will be performed using Pearson Chi-Square test or Fisher's exact test.

Association between type of core agent initiation and changes in BMI:

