Adjusted linear regression models will be used to assess the association between core agent and mean changes in BMI at 6, 12, and 24 months. Baseline variables included in the adjusted model will be selected a priori, based on the literature, including baseline age, sex, race/ethnicity, comorbid conditions and concomitant medications associated with weight gain and weight loss [33, 34], as well as change in viral load and CD4 cell count. Factors associated with the exposure and the outcome identified in the descriptive analyses will be considered for inclusion in the adjusted model if the requirements for confounding are met. Inverse probability-of-censoring weights will be used to account for patients who discontinue treatment or are lost to follow-up and constructed using a logistic regression model.

*This analysis will be stratified by baseline BMI categories (underweight, normal weight, overweight, obese).

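### Dating loss to follow-up 12 months after last contact leaves the censoring weights with no loss events at month 6, none or few at month 12, and only part of the loss at month 24

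*Protocol*

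**What the plan says.** Four rules in the protocol bear on this.

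- **Dating of loss (section 8.1).** A patient counts as clinically active with one or more clinic visits per 12 months. The rule for the others is: "Patients failing to meet the continuous clinical activity requirement will be censored 12 months after their last contact". Follow-up is counted from the day the patient's first eligible regimen starts, on or after the DTG approval date.
- **Analysis set (section 8.5).** At each of months 6, 12 and 24, "the study population will be restricted to patients with a follow-up greater or equal to that time point".
- **Weights (section 8.5.1, BMI association).** "Inverse probability-of-censoring weights will be used to account for patients who discontinue treatment or are lost to follow-up". They come from a logistic regression.
- **Outcome windows (section 8.3.2).** Month 6 uses the "BMI measured the closest to 6 months after core agent initiation, between >3 and ≤9 months"; month 12 uses the "BMI measured the closest to 12 months after core agent initiation, between >9 and ≤15 months". The month-24 window runs from >21 to ≤27 months.

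On missing values, section 8.5.1 says in its descriptive part: "The denominator for proportions will be patients tested, excluding those with missing values". It states no rule for a missing follow-up BMI in the regression.

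**The concern.** Censoring weights work by up-weighting patients who remain, so that they stand in for similar patients who were censored. They can do this only for patients whom the data set marks as censored.

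Under the 12-month rule, a patient who stops attending soon after the index date is still marked as in follow-up at month 6, and usually at month 12. The weight model counts that patient as retained, yet there is no BMI in the window from which to form a change. The patient contributes no outcome, and nobody is up-weighted in their place.

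This affects the second primary objective, the comparison of BMI change between DTG and the other core agents, which section 6.2 says is to support a safety signal evaluation. A reader of the results would take the estimates as corrected for loss to follow-up at all three time points.

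**Working it through.** The protocol states no loss rate and no missing-BMI rate, so there is no figure of its own to reproduce. The check is date arithmetic on its rules.

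**Inputs.** Let t be the month of last contact, counted from the index date, and T the time point.

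- Loss date = t + 12 (section 8.1).
- Kept in the analysis set if t + 12 ≥ T, that is t ≥ T − 12 (section 8.5).
- In-window BMI impossible if t is no later than the opening of the window: 3, 9 or 21 months (section 8.3.2).

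**Result, with the index prescription counted as a contact (t ≥ 0).**

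| T | Counted as lost | In-window BMI impossible | Counted as followed, BMI impossible |
|---|---|---|---|
| 6 | t < −6: nobody | t ≤ 3 | t from 0 to 3 |
| 12 | t < 0: nobody | t ≤ 9 | t from 0 to 9 |
| 24 | t < 12 | t ≤ 21 | t from 12 to 21 |

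At T = 12, a patient never seen after the index date has a loss date of exactly 0 + 12 = 12, and the greater-or-equal rule keeps that patient.

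**Result if the index prescription is not a contact.** Baseline BMI needs a weight taken on or within 3 months before the index date (section 8.3.2), so t is at least −3 and the earliest loss date is −3 + 12 = 9. Month 6 still has no loss events. Month 12 can have a few: patients not seen from the index date onward, with loss dates from about month 9 to before month 12.

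**Illustration under assumed loss rates.** Assume a constant annual loss a of 5%, 10% or 20%. The share with last contact by month m is 1 − (1 − a)^(m/12), and the index date is taken as a contact.

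| T | In-window BMI impossible (m = 3, 9, 21) | Counted as lost (m = 0, 0, 12) |
|---|---|---|
| 6 | 1.3%, 2.6%, 5.4% | 0% |
| 12 | 3.8%, 7.6%, 15.4% | 0% |
| 24 | 8.6%, 16.8%, 32.3% | 5%, 10%, 20% |

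At month 24 the weights thus see about 58% to 62% of the relevant loss (5/8.6 = 0.58; 20/32.3 = 0.62). The loss rates are assumptions; the zeros at month 6 hold whatever the rate.

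**What a shift could look like (assumed inputs).** The bias in one agent's mean is the share unmeasured times the difference in mean change between unmeasured and measured patients. Suppose that difference is 0.3 to 0.5 kg/m². The month-12 shares above then give 0.038 × 0.3 = 0.01 to 0.154 × 0.5 = 0.08 kg/m² for one agent. Only the imbalance reaches a contrast: if the unmeasured share differs by 10 percentage points between two agents, the contrast shifts by 0.1 × 0.3 = 0.03 to 0.1 × 0.5 = 0.05 kg/m². For scale, in the cohort of ART-experienced patients cited in section 6.1, the 12-month mean changes are DTG 0.30, RAL 0.24, EVG 0.23, DRV 0.41 and RPV 0.06. The differences from DTG are therefore 0.06 to 0.24 kg/m² in absolute size.

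**The case against.** **The weight model's event is not defined.** Section 8.5.1 does not say that the indicator copies the section 8.1 censoring date, and an analysis plan that is not shown could define it differently. That is fair, and the fix below is compatible with the section as worded. But the protocol does fix the loss date, the analysis set and the purpose of the weights. An analysis plan that follows all three inherits the conflict.

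**The weights still do something.** A reader might infer that the plan has no working protection at months 6 and 12. The documents do not support that. Core agent discontinuation is a separate censoring event in section 8.1, it can occur before either time point, and the weights cover it. If a lapsed prescription is recorded as discontinuation, some patients who leave care would be caught that way; the protocol does not say how discontinuation is dated.

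**Month 12 is less certain than month 6.** A reader might also infer that loss by month 12 is impossible on any reading. It is not: activity is defined by clinic visits, whereas the index date is a prescribing date.

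**Complete-case handling is inferred.** The sentence on excluding missing values concerns denominators of proportions in the descriptive analyses, not the regression. It remains true that a change in BMI cannot be formed without a follow-up BMI, and no other handling is stated.

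**No material bias is shown.** This also stands. The protocol supplies neither a loss rate nor a difference in BMI change, and missingness explained by agent and the adjusted covariates does not bias the contrast if that model is right.

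**Conclusion.** The point holds as a conflict between stated rules. The loss component of the weights is empty at month 6, empty or nearly so at month 12 (empty if the index prescription is a contact), and partial at month 24, where loss after month 12 but before the window opens goes uncounted. This assumes that the weight model uses the section 8.1 loss date.

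The documents do not show that the comparison is materially biased. The figures in kg/m² above rest on assumed inputs, and a shift in one agent's mean must not be read as a shift in the DTG contrast. The contrast is affected only where missingness, or its relation to BMI change, differs by agent beyond what the covariates explain. What can be said is that the correction announced for loss would be largely absent at two of three time points. That should be put right before analysis.

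**What to change.** For the weights, define the event as having a BMI recorded in the window while still on the core agent, yes or no, among all patients whose window closes by study end. Model it by logistic regression on agent and baseline covariates, and weight the measured patients by the inverse of the fitted probability. This covers loss, discontinuation and plain non-measurement in one indicator. It still assumes that, given those covariates, being measured is unrelated to BMI change.

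If a smaller change is preferred, date loss at last contact for the weight model and leave the rest as it is. That covers loss but not patients who attend without being weighed.

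In either case, report the share without an in-window BMI by agent and time point, and say whether the index prescription counts as a contact.

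The cost is a few sentences of protocol or analysis plan wording and a different indicator in the same logistic model. No new data are needed. The weights will be somewhat more variable.

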8.2. Study Population and Setting

The analysis population will be identified from the OPERA Observational Database according to the inclusion criteria defined below.

Primary population

1) A diagnosis of HIV-1, a positive HIV-1 Western Blot, or a positive HIV-1specific ELISA; and a detectable HIV-1 viral load test

- 2) At least 18 years of age at the index date
- 3) Male or female patients
- 4) Prescribed DTG, RPV, RAL, BIC, EVG/c and DRV(/r/c) as part of a 3-drug regimen for the first time between 01AUG2013 and 31DEC2017
- 5) Not exposed to >1 core agent of interest concurrently

Subjects with the following criteria will be excluded from the study sample:

- 1) HIV-negative
- A diagnosis of HIV-2, a positive HIV-1/HIV-2 Multispot, a positive HIV-2specific ELISA, a positive HIV-2 Western Blot or a detectable HIV-2 viral load test
- 3) Women who are considered pregnant at the index date
- 4) Transgender patients (potential for weight changes due to hormone use)

Secondary population

The study population for the secondary objectives will be a subset of the primary study population meeting the following additional inclusion criteria:

- Patients switching to DTG, RPV, RAL, BIC, EVG/c or DRV(/r/c) as part of a 3-drug regimen for the first time between 01AUG2013 and 31DEC2017 (excluding ARTnaïve patients)
- Patients with a viral load <200 copies/mL at last viral load test prior to switch to core agent of interest

The descriptive primary objective (1) will be stratified by prior ART exposure (ART-naïve and ART-experienced. The primary objective assessing association between core agent and BMI change (2), and the secondary objective will be restricted to ART-experienced patients. ART-experienced will be defined as history of ART prior to initiation of the core agent of interest, or a baseline viral load of <1000 copies/mL.

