8.4. Data sources

The OPERA[®] (Observational Pharmaco-Epidemiology Research & Analysis) database and research network is a multi-site observational database built from the complete patient health records managed in Electronic Health Record (EHR) systems from more than 400 participating caregivers 81 separate locations throughout the U.S. (see coverage map below).

Through their membership in OPERA, medical practices meet the Centers for Medicare & Medicaid Services (CMS) Electronic Health Record (EHR) Incentive Program for Integration with a Specialized Registry. OPERA-participating physicians and ancillary healthcare providers have documented the care of over 800,000 patients in their EHRs, including 80,000 HIV+ patients of which 14.8% are women, representing 7 percent of all the HIV+ patients linked to care in the U.S. The OPERA database is refreshed from these EHR databases at each clinic on a daily basis, making the OPERA database the largest continuously operating cohort of HIV+ patients in the U.S.

In total, there are more than 2.5 million documented prospective visits in the EHR systems for these HIV+ patients and 2.6 million prescriptions written for ART medications. The average years of follow-up (years of documenting patient visits prospectively in the EHR) for patients in OPERA is 4.2 years and there are 5,479 HIV+ patients who have nine years or more of follow-up.

In addition to HIV treatment, OPERA captures the diagnosis and treatment of co-morbid conditions and diagnoses of HIV negative patients. Epividian analyses other serious co-morbid conditions such as Hepatitis C with about 8% of HIV+ patients in OPERA co-infected.

Figure 1.. U.S. Map of OPERA HIV+ Population & CDC (2010) State-by-State Estimates

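### Pregnancy is excluded only on the index date, but baseline BMI may use a weight from up to 3 months earlier, so a few women can enter with a pregnancy weight as baseline

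*Protocol*

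**What the plan says.** Exclusion 3 in protocol section 8.2 removes "Women who are considered pregnant at the index date". It refers to a single day.

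Section 8.3.2 defines the baseline for the main outcome over a longer span: "Baseline BMI identified using weight measured within 3 months prior to or on index date". Change in BMI is follow-up BMI minus this value. The first follow-up value is the "BMI measured the closest to 6 months after core agent initiation, between >3 and ≤9 months".

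Section 8.1 makes pregnancy a censoring event during follow-up. On baseline data it adds: "Data from the visit closest to the index date will be used for analysis". Section 8.3.3 repeats that rule for the covariates.

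Section 8.5.1 adjusts the BMI model for variables "including baseline age, sex, race/ethnicity, comorbid conditions and concomitant medications associated with weight gain and weight loss", together with change in viral load and CD4 count, and stratifies by baseline BMI category. Recent pregnancy or delivery is named neither there nor in the covariate list of section 8.3.3.

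**The concern.** The protocol already treats pregnancy as making weight unusable: it excludes pregnancy at index and censors it afterwards. It also excludes transgender patients because hormone use may alter their weight. The one stretch of time left uncovered is the 3 months that can supply the baseline weight.

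A woman weighed while pregnant, whose pregnancy then ends and who starts a core agent within 3 months of that weighing, meets every eligibility criterion. Three results inherit the wrong baseline:

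- her change in BMI and weight at 6, 12 and 24 months;
- her baseline BMI stratum in the regression model;
- her row in the table of BMI category changes (Table 1).

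The study is meant to inform a weight-gain signal for DTG (section 6.2). A false fall would mask gain if it were more frequent among DTG users, and would exaggerate the DTG contrast if it were more frequent among users of a comparator.

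**Working it through.** **Does any rule close the gap?**

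- Censoring at pregnancy ends follow-up after index. It cannot change a baseline taken before index.
- Using the nearest visit to index helps when there is a weight after the pregnancy ended. It does not help when the last weight in the window was taken before that.
- Adjustment for age and sex does not identify the affected women.

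So the gap is open, and the question is its size.

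**The plan's own figures.** No stated figure is in dispute. Table 2 (section 8.5.3) serves only as a yardstick, and it reproduces. The check was an F test with 4 and N − 15 degrees of freedom, noncentrality N·ρ²/(1 − ρ²), 80% power, and alpha 0.05 (assumed, as it is not stated). It gives N = 29,832 at ρ = 0.02, 822 at ρ = 0.12 and 292 at ρ = 0.20. The smallest tabulated difference in mean BMI is 0.04, taken here at face value as kg/m².

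**Inputs from the protocol**

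- Share of women, section 8.4: "including 80,000 HIV+ patients of which 14.8% are women". That the share also holds in the study cohort is an assumption.
- ART-experienced new users with a baseline BMI, section 8.5.3: 17,370.

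**Inputs assumed, because the protocol gives none**

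- q, the share of women whose baseline is a pregnancy weight: 1–2%; wider range 0.5–5%.
- e, the excess BMI at baseline: 8 kg at a height of 1.62 m, so 8 / 1.62² = 3.05 kg/m²; wider range 1–5 kg/m².

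**Number of women**

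- 0.148 × 17,370 = 2,571 women.
- 1% is 26 women; 2% is 51 women.

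**Shift in mean BMI change**

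- Among women: 26 × 3.05 / 2,571 = 0.03; 51 × 3.05 / 2,571 = 0.06 (downward).
- Whole cohort: 26 × 3.05 / 17,370 = 0.005; 51 × 3.05 / 17,370 = 0.009 (downward).
- Wider range, formula 0.148 × q × e: from 0.148 × 0.005 × 1 = 0.0007 to 0.148 × 0.05 × 5 = 0.037. Among women alone (q × e), it runs from 0.005 to 0.25.

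**Bias in the DTG contrast.** Error common to all agents cancels. The difference in q between two agent groups that would produce a bias of 0.04 is 0.04 / (0.148 × e):

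| e (kg/m²) | Difference in q among women |
|---|---|
| 2 | 13.5 percentage points |
| 3 | 9.0 percentage points |
| 5 | 5.4 percentage points |

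**Misplacement of stratum.** For one affected woman, 3.05 kg/m² is about 61% of the 5-unit overweight band (3.05 / 5). It can therefore move her up one category at baseline and later produce a false move down.

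**The case against.** The strongest reply is that few such women exist. Under sections 8.1 and 8.3.1, index is the first listed core agent after 01AUG2013, and earlier use of another listed agent within OPERA is not allowed. A woman who starts a listed agent while pregnant has her index then and is excluded. One who was already on a listed agent is censored when she becomes pregnant. A switch between listed agents after delivery creates no new index. What remains is women with no listed agent in OPERA through the pregnancy who first receive one within 3 months of its end. Some of them will have a weight taken after the pregnancy, and early losses involve little weight. All of this stands. The assumed 1–2% takes no account of the new-user rule, and 8 kg is not typical of every case.

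It can also be said that baseline definitions may be refined in the analysis specifications mentioned in section 8.6, and that nothing here is a misstatement. It is indeed not a contradiction. But the exclusion and the baseline window are both fixed in the protocol, and as written they do not match.

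A reader might go further and infer that women start particular agents around delivery, so that the error gathers in one group and distorts the DTG comparison. The documents contain nothing on when women change regimen relative to delivery, and no counts of women by agent. Nor do they plan a women-only analysis in which a larger shift would appear: sex is an adjustment variable, and the strata are BMI categories.

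**Conclusion.** The gap is real: an eligible woman can have a pregnancy weight as baseline BMI, which gives a false fall in BMI and possibly too high a stratum. Its effect is small. With 14.8% women, 1–2% of them affected and about 3 kg/m² each, the shift is at most about 0.06 kg/m² among women and under 0.01 overall. Even the extreme of the wider range, 0.037, stays below the smallest difference in Table 2. All these sizes rest on assumed frequencies and weights.

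The documents do not support the claim that the DTG contrast is materially biased. That would need the affected share among women to differ between agents by roughly 5 to 14 percentage points to reach 0.04. The reason to act is that identifiable patients would carry a wrong baseline, and that preventing it costs almost nothing. It is a minor improvement.

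**What to change.** Either of two one-line changes would do:

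- in section 8.2, extend exclusion 3 to women pregnant at any time in the 3 months before index or on the index date, so that it covers the baseline weight window; or
- in section 8.3.2, state that a weight taken during pregnancy may not serve as the baseline.

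Both remove the pregnancy weights. The second keeps women who have a usable weight after the pregnancy ended.

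The cost is at most a few dozen women (26 to 51 on the assumptions above, fewer once the new-user rule is counted). Neither change removes all retained postpartum weight. If the sponsor wants to address that too, a postpartum period before index would have to be stated.
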